## 2 SYNOPSIS

Protocol Number	SD-001
Protocol Title	Safety and Effectiveness Evaluation of the Sinusway™ Device for Endoscopy of the Nasal Cavity and Paranasal Sinuses in Conjunction with Sinus Balloon Dilation
Participating Countries	USA
Clinical Phase	Open, multi - center, prospective, feasibility study
Investigational Study Device	Sinusway™, a flexible, steerable endoscope, by 3NT Medical Ltd.
Study Procedures	Up to 15 Patients scheduled for sinus balloon dilation will be examined with Sinusway™ before and as part of balloon sinus dilation in the operation room (OR) or office setting (Office). The patients will attend the following: 1. Visit 1: Screening and Enrollment, as part of pre-operative visit 2. Visit 2: Sinusway evaluation at the time of the procedure
Study Population	15 adult patients, male or female, scheduled for Sinus Balloon Dilation.
Study Purpose	To assess the safety and initial performance of Sinusway™ in patients in terms of access and visualization of the nasal anatomy and paranasal sinuses, usability (alone and in conjunction with balloon dilation instruments), visualization quality, and irrigation.
Study Endpoints	
Primary – Safety Endpoints:
 
 
• Device related adverse events
 
 
Secondary – Performance Endpoints:
 
 
• To evaluate the ability to access and visualize the nasal anatomy including the maxillary, frontal, and sphenoid sinuses.
 
• To evaluate usability by filling a user questionnaire
 
• To evaluate irrigation of the nasal anatomy
 

Inclusion/Exclusion Criteria	
Inclusion Criteria:
 
 
1. Male or female patient indicated for balloon sinus dilation procedure by the ENT specialist
 
2. Patient age: adult (>18 years old)
 
3. Patients in general good health in the opinion of the investigator as determined by medical history and physical examination
 

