### 4.1 Safety assessment

Safety assessment will be based upon monitoring the adverse device effects, which will be collected throughout the procedure.

All adverse events and serious adverse events will be reported in accordance with reviewing Ethics Committee /Institutional Review Board (IRB), FDA and Competent authority requirements.

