#### **4.3 Study End Points**

##### **Primary - Safety**

All adverse device effects will be captured and summarized as defined in **Section-8**. Adverse device effects (type, frequency, severity) are expected to be similar to those reported in literature for Nasal Endoscopy (section 8).

For this study, the Safety comparison with the data of Nasal Endoscopy reported in literature will be descriptive with no statistical endpoints.

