### Visit 2: Procedure and Study Termination

- **Before the procedure:**
  - Eligible subject/s will attend the Medical Center at the day of procedure and will be inquired by the PI regarding changes to their health status since the screening visit. If at this point it is determined that the patient **does not** meet all Inclusion and Exclusion criteria and cannot be treated, the patient will be exited from the study. These patients will be considered screening failures, and will not be included in any of the safety or efficacy endpoint analyses.
- **Endoscopy:**
  1. Patients may undergo BSD under local anesthesia, intravenous sedation and local anesthesia or under general anesthesia, at physician discretion.
  2. The Sinusway device will be prepared for use per its instructions for use.
  3. Evaluation of the patient with physician's typical rigid endoscope(s). Visualization of the sinuses (frontal, maxillary, sphenoid) will be recorded as performed/failed and an Image of the anatomic landmark will be taken.

4. Following the Evaluation with physician's typical rigid endoscope(s) the evaluation will be repeated using the Sinusway endoscope. Access to the sinuses (frontal, maxillary, sphenoid) will be recorded as performed/failed and an Image of the anatomic landmark will be taken. Nasal Cavity and sinuses inflammation score will be captured using the Lund Mackay CT and endoscopy score.
5. BSD procedure will be performed with either endoscope.
6. Irrigation of the nasal anatomy will be performed and recorded as Done/Not Done and which sinus was irrigated.
7. Following the BSD procedure, repeated evaluation of patient's sinuses and nasal cavity will be performed using the Sinusway endoscope
8. Usability assessment will be completed by physician.
9. If applicable, patient pain assessment using a 0-10 pain Scale and patient tolerability will be captured (Office procedures only)

- **After the procedure:**
  - The patient will recover from the procedure per physician's common practice. Before patient's release, recording of AE, if any, will be performed. Patient will exit the study.

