Definitely	There is evidence of exposure to the test procedure/device , the AE is most likely to be explained by the test procedure / device than by another cause; the challenge is positive; rechallenge (if feasible) is positive; the AE shows a pattern consistent with previous knowledge of the test procedure / device.

Degree	Description
Probably	There is evidence of exposure to the test procedure / device; the temporal sequence of the AE onset relative to the test procedure / device is reasonable; the AE is more likely explained by the test procedure / device than by another cause.
Possibly	There is evidence of exposure to the test procedure / device; the temporal sequence of the AE relative to the test procedure / device is reasonable; the AE could have been due to another equally likely cause;
Probably not	There is evidence of exposure to the test procedure / device; there is another more likely cause of the AE
Definitely not	The patient did not receive the test procedure / device; or temporal sequence of the AE onset relative to test procedure / device is not reasonable; or there is another obvious cause of the AE.

**Action taken** - whether or not the adverse event caused the subject to be discontinued from the study.

**Clinical Outcome** – whether the adverse event was resolved or ongoing.

All adverse events, including a worsening of physical examination findings, in comparison with baseline values, must be followed until the event resolves, the condition stabilizes, the event is otherwise explained, or the patient is lost to follow-up.

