## 8.6 Adverse Event Reporting

It is the responsibility of the investigator to document all treatment related and device related Adverse Events (ADE's), which occur during the course of the study. All ADEs will be recorded on the adverse events page of the CRF. Severity and relationship to study device will be assigned by the investigator as described in the section above. ADEs will be recorded after the subject has been admitted to the clinic Visit-2.

Any SAE, whether deemed device-related or not, must be reported to the site Ethics Committee and to the sponsor as soon as possible after the investigator has become aware of its occurrence even if not all the information is available at the time of initial contact.

The investigator must complete a SAE Form, and send it to the Sponsor within 24 hours of becoming aware of the event. Accompanying documentation, such as copies of hospital case reports, autopsy report, and other documents when applicable, should be sent as soon as they are available.

The site's Ethics Committee must also be duly notified and dealt with, according to the Hospital and FDA/Ministry of Health regulations. Subjects who have had a SAE must be followed clinically until all parameters (including laboratory) have either returned to normal or are stabilized.

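### The primary safety endpoint promises all adverse device effects, but recording stops at release on the procedure day and no later contact is planned

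*Protocol*

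**What the plan says.** The primary endpoint in Protocol section 4.3 reads "All adverse device effects will be captured and summarized as defined in" Section 8. The synopsis gives it as "Device related adverse events". Neither states a time window.

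The window has to be put together from other places:

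- **Start.** Section 8.6: "ADEs will be recorded after the subject has been admitted to the clinic Visit-2".
- **End.** Section 6.2, Visit 2: "Before patient's release, recording of AE, if any, will be performed. Patient will exit the study".
- **Schedule.** Table 1 marks adverse events and patient exit at Visit 2 only, and Visit 2 is its last column.
- **Duration.** The synopsis puts per-patient participation at 1 to 30 days, all of it between the pre-operative visit and the day of the procedure.
- **A narrower version.** Section 4.1 bases the safety assessment on "monitoring the adverse device effects, which will be collected throughout the procedure", which leaves out recovery.

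Two rules reach past release, both for events already known. Section 8.2 says adverse events "must be followed until the event resolves, the condition stabilizes, the event is otherwise explained, or the patient is lost to follow-up". Section 8.6 says "Subjects who have had a SAE must be followed clinically until all parameters (including laboratory) have either returned to normal or are stabilized". Section 8.6 also requires any serious adverse event to be reported "as soon as possible after the investigator has become aware of its occurrence".

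**The concern.** An endpoint described as all adverse device effects invites the reading that delayed effects were looked for. Under this schedule no patient is asked about them.

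The gap touches effects that the protocol itself expects. Section 8.2 lists the anticipated adverse device effects and refers to section 8.1 for detail. That section describes several in terms of the time after surgery: bleeding during or after the operation, voice change, blockage when cartilage shifts, and scar bands that the surgeon removes at later visits. This study has no such visit.

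Safety is the primary endpoint, and section 6.1 says the information may inform device modification and later controlled studies. A report of no adverse device effects could be carried forward as broader reassurance than the data give.

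**Working it through.** The protocol gives no power, error rate or derivation for its 15 patients, so there is no stated figure to reproduce. The check has two parts.

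**1. Anticipated effects set against the observation window (admission to release)**

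| Anticipated effect (8.2) | Timing in 8.1 | Can it first appear after release? |
|---|---|---|
| Nasal obstruction, including scar bands | Cartilage shifts after surgery; bands removed at postoperative visits | Yes, this is the clearest case |
| Voice change | After sinus surgery | Possibly; onset relative to release not given |
| Bleeding | About 2%, during and after the operation combined | Possibly; the split is not given |
| Mucosal injury | Cited data assessed at the end of the procedure | The cited data fit the window |

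Scheduled adverse event contacts after release: 0, for up to 15 patients.

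**2. What a later contact could show**

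Let p be the proportion of patients with a non-serious effect that first appears after release, and n the number of patients asked later. Then

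P(at least one case seen) = 1 − (1 − p)^n.

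The protocol gives no value of p for this device, so the values below are assumptions. The 12 reached of 15 is also an assumption.

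| Assumed p | Current plan, n = 0 | n = 12 | n = 15 |
|---|---|---|---|
| 2% | 0 | 1 − 0.98^12 = 22% | 1 − 0.98^15 = 26% |
| 5% | 0 | 1 − 0.95^12 = 46% | 1 − 0.95^15 = 54% |
| 10% | 0 | 1 − 0.90^12 = 72% | 1 − 0.90^15 = 79% |
| 20% | 0 | 1 − 0.80^12 = 93% | 1 − 0.80^15 = 96% |

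The zeros refer to planned data collection for non-serious effects. A serious event could still be reported if the investigator happened to learn of it.

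**Using the sinus-surgery rates in section 8.1.** Let r be a cited rate and s the share of those events that first appear after release. The protocol does not give s, so it is varied. The chance of recording at least one event in 15 patients by release is 1 − (1 − r(1 − s))^15.

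| Cited rate r | s = 0 | s = 0.25 | s = 0.5 | s = 0.75 | s = 1 |
|---|---|---|---|---|---|
| Bleeding, 2% | 26.1% | 20.3% | 14.0% | 7.2% | 0% |
| Minor complications, 5% | 53.7% | 43.6% | 31.6% | 17.2% | 0% |

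The loss depends on s. When s = 1 the probability is zero whatever the sample size, so enrolling more patients would not close the gap.

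**The case against.** The strongest reply is that the window is already defined. Section 4.3 defers to Section 8, and section 8.6 confines documentation to events during the course of the study, which ends at release. On that reading the endpoint takes its window by reference and only clarity is lacking. The reading is possible, but neither the endpoint nor the synopsis states the limit, and section 4.1 gives a different one.

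Second, after surgery does not mean after release. Recovery is partly observed, and the bleeding and voice text gives no onset relative to release. This stands: only the obstruction and scar-band text points clearly to a later time.

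Third, section 8.1 describes sinus surgery, and says it is included because the endoscope is used with balloon dilation. That is true, but section 8.2 adopts the list as anticipated device effects.

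Fourth, the comparator named in section 4.3 is nasal endoscopy, and the mucosal data in section 8.1 were assessed at the end of the procedure. This also stands: that part of the comparison fits the window. The 2% bleeding figure, which includes postoperative events, does not.

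Fifth, 15 patients in a single arm will rarely allow a late event to be attributed to the endoscope rather than to the dilation, and no document supports delayed rates of 10% or 20%. Both points limit what an added contact can deliver. They do not provide a route for detecting a new non-serious effect after release.

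The follow-up rules in sections 8.2 and 8.6 are compatible with exit at release, since follow-up of a known event can continue afterwards. Only the exception is missing from section 6.2.

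**Conclusion.** The concern holds and should be fixed. Followed as written, the plan yields a primary safety result that cannot include non-serious effects first appearing after release, while the endpoint is worded as though it could. The conclusion rests on the schedule and the protocol's own risk text and needs no assumed rate.

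The size does depend on assumptions. For delayed effects in 5% to 20% of patients, one complete later contact raises the chance of seeing at least one case from 0 to between 54% and 96%. At 2% it reaches only 26%. A clean result would therefore support peri-procedural safety, and even with a later contact it would say little about rare delayed effects.

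**What to change.** **Preferred.** Add one adverse event contact after the procedure, by telephone or from the routine postoperative visit, at a time the sponsor fixes in the protocol. Add it as a column in Table 1, move patient exit to it in section 6.2 and Table 1, and update the per-patient duration in the synopsis. The cost is up to 15 contacts, one CRF page and longer participation per patient. Attribution of late events will often remain uncertain.

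**Otherwise.** Restate the primary endpoint in section 4.3 and the synopsis as device-related adverse events from Visit 2 admission to release. Align section 4.1 with that window, limit the literature comparison to rates observed over a matching window (such as the end-of-procedure mucosal data in section 8.1), and state that delayed effects are not assessed. This costs wording only, but leaves delayed effects unexamined.

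**In either case.** Add a sentence to section 6.2 saying that a patient with an event still open at exit continues to be followed as sections 8.2 and 8.6 require.

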## 6.3 Methods and Timing for assessments

Schedules of assessments are listed in **Table No. 1 below**.

**Table 1: Study visit schedule**

Study Activities	Session I: Screening and Inclusion V-1	Session II: Procedure V-2 Within 30 days post screening
Informed Consent	x	
Demographic Data	x	
Medical History	x	
SNOT 20	x	
Concomitant medication	x	
Physical Examination	x	
Laboratory test (Optional as commonly done for BSD)	x	
Vital Signs (optional)	x	
Inclusion/exclusion criteria	x	
CT scan (as commonly done for BSD)	x	
Lund Mackay/Kennedy inflammation score	x	x
Endoscopy with Sinusway and Commercially Available Endoscope		x
Balloon sinus dilation Followed by Sinusway Endoscopy		x
User questionnaire		x
Patient tolerability and pain score		x
AEs/SAEs		x
Patient Exit		x

## 7 STATISTICAL CONSIDERATIONS AND SAMPLE SIZE

### Statistical Considerations

No statistical analysis will be used as this is a feasibility safety study.

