## 6 INVESTIGATION PLAN

### 6.1 Study Design

#### Type of Study

This is an open, multi-center, prospective, feasibility study in which the investigational device, the Sinusway, will be tested in a single group of adult patients, male or females.

The rationale behind this feasibility study is to show that access and visualization of the nasal anatomy and paranasal sinuses (Maxillary, Frontal and Sphenoid sinuses) in conjunction with Balloon Sinus Dilation in patients suffering from symptoms attributable to sinusitis is feasible in the office and operating room settings; This is an essential step in the development of a combined dilation and visualization system that will allow visualization, dilation and lavage of the sinuses via their natural ostia during an office visit, and minimize radiation exposure, antibiotic use, multiple office visits, and cost.

This study is proposed after completing a series of clinical cases, which demonstrated that the system is safe and performed well to physician's satisfaction (detailed information on the studies is provided in the Investigator's Brochure).

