### Sample Size

Up to Fifteen (15) patients are expected to complete the study at all sites

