### Risk associated with Endoscopic Sinus Surgery

Surgeons performing routine endoscopic interventions are faced with minor complications in 5% and major complications in 0.5–1% [21]

- Infection- A patient with sinusitis is at risk of developing infection (abscesses, meningitis, etc.) Infection risk increases with the invasiveness of the intervention. The rate of intracranial infections where the intervention is maximized is 1.6% and the rate of infection-related mortality is 0.125%. It is comparable to the one of transcranial surgeries not involving the use of an endoscope [5,6,7]. The Risk of Infection following Sinusway use is mitigated since the Sinusway endoscope is a disposable intended for single use only.
- Bleeding- Bleeding may occur, particularly in susceptible patients with increased risk of bleeding, such as those receiving aspirin or other anticoagulant medications (i.e. Plavix, Coumadin, etc.) [20]. The rate of peri- or postoperative bleeding is around 2% altogether; transfusions were required in about 0.2% of cases [8,9].

- Nasomucosal injury- Nasomucosal injury may occur during transnasal endoscopy. Nasomucosal injury was assessed in 1569 patient that underwent unsedated transnasal esophagogastrroduodenoscopy (EGD), at termination of the procedure. Normal mucosa was observed in 68% of cases, redness of mucosa was observed in 19% of cases, oozing hemorrhage was observed in 12% of cases and overt bleeding was observed in 2% of cases. The hemorrhage was self-limiting and no patient required nasopharyngeal treatment [10].

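### The primary safety endpoint is planned as a bare count: section 4.3 expects ADE frequency similar to the literature, section 7 excludes any statistic, and 15 patients cannot establish similarity for most quoted rates

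*Protocol*

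**What the plan says.** Section 4.3 (Primary - Safety) sets the expectation: "Adverse device effects (type, frequency, severity) are expected to be similar to those reported in literature for Nasal Endoscopy (section 8"). Frequency is therefore one of three named features of the comparison. No margin or tolerance is given. The same section limits the status of the comparison: "For this study, the Safety comparison with the data of Nasal Endoscopy reported in literature will be descriptive with no statistical endpoints".

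Section 7 (Statistical Considerations) says: "No statistical analysis will be used as this is a feasibility safety study". The synopsis marks its statistical analysis plan entry as not applicable. The exclusion is therefore the protocol's own statement and not a detail left to another document.

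Section 7 (Sample Size) says: "Up to Fifteen (15) patients are expected to complete the study at all sites". The figure is a ceiling, and no reasoning is attached to it.

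Section 8.1, to which section 4.3 points, supplies the rates, among them:
- "Surgeons performing routine endoscopic interventions are faced with minor complications in 5% and major complications in 0.5–1"%
- "The rate of peri- or postoperative bleeding is around 2% altogether"
- for nasomucosal injury in 1569 transnasal esophagogastroduodenoscopies (EGD), "oozing hemorrhage was observed in 12% of cases and overt bleeding was observed in 2% of cases", with redness in 19%.

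**The concern.** A descriptive comparison of frequencies still needs some indication of how precisely the study's own frequency is known. The plan sets an expectation about frequency for the primary endpoint and then excludes the one simple quantity that would show how little 15 patients can say about it. A result such as 0/15 placed beside a published 5% or 1% gives no sign of which rates have been excluded. What is at stake is the conclusion the study may draw on its primary endpoint: whether it may say that ADE frequency resembles the literature, or only how many ADEs were seen and which rates remain compatible with that count.

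**Working it through.** **Inputs.** n = 15 (section 7, a maximum). Comparison rates from section 8.1: 5% minor, 0.5–1% major, 2% bleeding, 12% oozing, 19% redness. The protocol gives no confidence level; 95% is assumed. It also gives no derivation of n = 15, so there is no planned figure to reproduce.

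**Step 1: upper limit after no events.** The exact limit solves (1 − p)^n = α.
- Two-sided 95% (α = 0.025): 1 − 0.025^(1/15) = 0.218, or 21.8%.
- One-sided 95% (α = 0.05): 1 − 0.05^(1/15) = 0.181, or 18.1%.
- If only 10 patients were treated, the two limits would be 30.8% and 25.9%.

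Other low counts, Clopper-Pearson two-sided 95%: 1/15 gives 0.2% to 31.9%; 2/15 gives 1.7% to 40.5%.

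**Step 2: the 0/15 limit against the quoted rates, and the chance of seeing nothing.** The ratio is the limit divided by the quoted rate. The last column is (1 − p)^15 with p set to the quoted rate.

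| Quoted rate | Ratio, two-sided limit | Ratio, one-sided limit | P(0 of 15) |
|---|---|---|---|
| Minor 5% | 4.4 | 3.6 | 46% |
| Bleeding 2% | 10.9 | 9.1 | 74% |
| Major 1% | 21.8 | 18.1 | 86% |
| Major 0.5% | 43.6 | 36.2 | 93% |
| Oozing 12% | 1.8 | 1.5 | 15% |
| Redness 19% | 1.15 | 0.95 | 4% |

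**Step 3: the chance of an event-free study when the true rate is above 5%.** At 10%, 0.90^15 = 21%. At 15%, three times the quoted minor rate, 0.85^15 = 9%. An event-free study is thus not rare at two to three times that rate.

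**Step 4: what the quoted rates measure.** Section 8.2 defines an ADE as an event related to use of the investigational device. Section 4.3 names nasal endoscopy as the comparator. The nasal endoscopy paragraph that opens section 8.1 contains no rates. The figures follow under the heading on endoscopic sinus surgery. They are mainly complications of the whole surgical procedure, plus the transnasal EGD series. They are not device-related rates for nasal endoscopy.

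**The case against.** The strongest objection is that sections 4.3 and 7 agree with each other. A reader might infer a contradiction between them, but section 4.3 itself makes the comparison descriptive, and both sections mean that nothing is tested. A single-group feasibility study of this size needs neither a test nor a power calculation, and section 6.1 says the results may feed device modification and later controlled studies. The protocol sets no success criterion and nowhere says that zero events would show safety. Anyone can compute an interval from the reported count. All of this stands. It does not remove the point, because an exact interval is itself descriptive and section 7, read literally, rules it out.

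Three stronger readings are not supported:

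- **That 0/15 leaves open several times every quoted rate.** This fails for oozing and redness. Section 8.2 lists nasomucosal injury among the anticipated ADEs. If such signs are counted, zero or one event is not the expected result either. At 14% (12% oozing plus 2% overt bleeding), P(0 or 1 of 15) = 0.86^15 + 15 × 0.14 × 0.86^14 = 36%. Whether they would be counted is not known.
- **That 15 patients cannot separate a 1% rate from a 20% rate.** For 0/15 the probabilities are 0.99^15 = 86% and 0.80^15 = 3.5%. The one-sided limit of 18.1% excludes 20%; only the two-sided limit includes it.
- **That section 6.1 over-reads eleven cases.** It says the study follows "after completing a series of clinical cases, which demonstrated that the system is safe", and section 3.4 describes eleven cases without a reported adverse event. Section 6.1 refers for details to the Investigator's Brochure, which is not available, so the two series cannot be assumed to be the same.

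**Conclusion.** The point holds in a limited form. The primary endpoint carries an expectation about frequency, while the plan provides no measure of precision for it. An event-free study of 15 would be compatible with true ADE rates up to 21.8%, so it could not establish similarity to the quoted 5%, 2% or 0.5–1% rates. For the 12% and 19% mucosal signs it would be more informative: rates of about twice those quoted would be excluded.

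This rests on the assumed 95% level, on all 15 patients being treated, and on counting patients with at least one ADE. The ratios show scale only, since the quoted rates mostly describe other procedures. The weakness is in reporting and interpretation. It is not an error of design or sample size.

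**What to change.** 1. **Section 7.** Replace the sentence that excludes analysis with: 'No hypothesis will be tested. The number of patients with at least one ADE, over all patients in whom Sinusway was inserted, will be given with an exact (Clopper-Pearson) 95% CI.' This also fixes the denominator. At present section 7 speaks of patients who finish the study, and section 13 allows some treated patients to be left out of the analysis.
2. **Section 4.3.** Remove frequency from the list of features expected to be similar, and add: 'With 0/15 the data are compatible with true ADE rates up to 21.8% (two-sided 95%); the study cannot establish similarity of frequency.'
3. **Section 4.3 or 8.1.** Note that the quoted rates come mainly from whole sinus surgery procedures or transnasal EGD and are not device-related rates for nasal endoscopy.

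The comparison stays descriptive. The cost is a few sentences and one calculation, with no added patients, visits or data. The price is a more modest statement on the primary endpoint. On the evidence available, section 6.1 should not be reworded.
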